8.7.5. Demographics And Baseline Characteristics Analysis

Demographics and baseline characteristics will be summarized using appropriate descriptive statistics.

8.7.6. Concomitant Medications/Therapies

All prior and concomitant medications recorded in the case report form will be coded to all matching Anatomic Therapeutic Classification codes using the most recent version of the WHO Drug Dictionary. Descriptive summaries will be prepared using the coded term. All concomitant medications recorded in the case report form will be listed.

8.7.7. Pharmacokinetic (PK) Analysis

The pharmacokinetic analyses and estimation of PK parameters will be performed using non compartmental methods using Phoenix® WinNonlin 8.3.1 or above.

8.7.8. Safety Analyses

8.7.8.1. Adverse Events

Adverse events will be classified by system organ class (SOC) and preferred term (PT) according to the most recent version of MedDRA dictionary.

TEAE are defined as adverse events with onset date on or after the first treatment. TEAEs will be summarized by treatment group, System Organ Class, and preferred term. The following TEAE summaries will be provided:

- a) Overall (i.e., regardless of severity or relationship to treatment)
- b) Adverse events by severity
- c) Related adverse events by severity

- d) Adverse events leading to treatment discontinuation by severity
- e) Adverse events leading to death by severity

8.7.8.2. Clinical Laboratory Data

Tabulations of raw data and change from baseline values will be presented by time point for each lab parameter. Tabulations will include the number of observations, mean, standard deviation, median, and minimum and maximum values. Abnormal laboratory results will be listed and summarized.

8.7.8.3. Vital signs

Tabulations of raw data and change from baseline values will be presented by time point for each vital sign parameter. Tabulations will include the number of observations, mean, standard deviation, median, and minimum and maximum values.

8.7.8.4. Physical Examination

Physical Examination findings will be presented as by-participant listing.

8.7.8.5. 12-lead ECG

Tabulations of raw data and change from baseline values will be presented by time point for each 12-lead ECG parameter. Tabulations will include the number of observations, mean, standard deviation, median, and minimum and maximum values.

8.7.8.6. Other Safety Data

All data from other tests such as unscheduled tests will be presented as a by-participant listing and/or summarized.

9. SAFETY REPORTING

The Investigator is responsible for the detection and documentation of events meeting the criteria and definition of an AE or SAE, as provided in this protocol. During the study when there is a safety evaluation, the Investigator or site staff will be responsible for detecting, documenting, and reporting AEs and SAEs as detailed in this Section of the protocol.

9.1. ADVERSE EVENT (AE) DEFINITION

An adverse event (AE) is defined as any unfavorable or unintended sign, symptom, or disease that occurs or is reported by the participant to have occurred, or a worsening of a pre-existing condition. An adverse event may or may not be related to the study treatment.

AEs will be elicited through direct questioning and participant reports. Any abnormality in physical examination findings or laboratory results that the investigator believes is clinically significant (CS) to the research participant and that occurred after initiation of the first study treatment will be reported as AEs. Abnormal findings that are NOT clinically significant should not be recorded as an AE.

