- **Follow-Up Visit 1 (FU1: Day 14)**
- **Follow-Up Visit 2 (FU2: Day 28)**

If any of the dose escalation stopping criteria have occurred in Part A or Part B, the SRC will make a final recommendation for dose escalation to the next cohort.

- **NOTE:** The dose escalation decision through the study will not be made until the following:
 - (1) All study participants in a given cohort have been enrolled,
 - (2) All such participants have completed Treatment Visit 5 (Day 7) (for SAD-Part A) and Treatment Visit 9 (Day 9) (for MAD-Part B) of the study or withdrawn from the study, whichever occurs first,
 - (3) The SRC will review the available safety data and recommend further dose escalation.

[figure not shown]
Additionally, dose escalation stopping criteria are defined per the below:

- a. Death in any participant in which the cause of death is judged to be possibly, probably or definitely related to MBS-COV.
- b. The occurrence in any participant of a severe local application site reaction (Grade 3 which doesn't resolve or recurs, or Grade 4) that is judged to be possibly, probably or definitely related to MBS-COV.
- c. The occurrence in any participant of a SAE whose causal relationship to MBS-COV is judged to be probably, possibly, or definitely related to MBS-COV.
- d. The occurrence, in two or more participants of Grade 3 AE or laboratory abnormalities, judged to be probably, possibly, or definitely related to MBS-COV.

- e. The occurrence of two of the same AE or laboratory abnormality \geq Grade 3 judged to be probably, possibly, or definitely related to receipt of MBS-COV
- f. The occurrence, in one or more participants of Grade 4 AE or laboratory abnormalities, judged to be probably, possibly, or definitely related to receipt of MBS-COV.
- g. Any pattern of significant symptoms, physical findings, or laboratory abnormalities that, although individually minor, collectively represent a safety concern in the opinion of the investigator and are judged by the SRC to be at least possibly related to MBS-COV.
- h. PK exposure limits of mean AUC of 385.6 h*ng/mL or C_{max} of 141.8 ng/mL for one cohort, whichever comes first.(Single dose: AUC of 386.9 h*ng/mL or C_{max} of 91.7 ng/mL).

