9.2.2. Toxicity Grading Scale (Intensity) Assessment

According to the guideline of “Toxicity Grading Scale for Healthy Adult and Adolescent Volunteers Enrolled in Preventive Vaccine Clinical Trials” issued by FDA, the severity of adverse events occurred in this study will be graded. The general guidelines for assessing the AE grade refer to appendix 1.

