9.2.3. Event Causality Assessment

AEs will be assigned a relationship (causality) to the study treatment. The Investigator will be responsible for determining the relationship between an AE and the study treatment. The type of event, organ system affected, and timing of onset of the event will be factors in assessing the likelihood that an AE is related to the study treatment. Relationship of AEs to study treatment will be classified as follows:

- 1. Definitely related:** This category applies to those AEs that the Investigator feels are incontrovertibly related to the study treatment. An AE may be assigned an attribution of definitely related if or when it meets all of the following criteria: (1) it follows a reasonable temporal sequence from administration of the study treatment; (2) it could not be reasonably explained by the known characteristics of the participant's clinical state, environmental or toxic factors, or other modes of therapy administered to the participant; (3) it follows a known response pattern to treatment with the study treatment.
- 2. Probably related:** This category applies to those AEs which, after careful medical consideration at the time they are evaluated, are felt with a high degree of certainty to be related to the study treatment. An AE may be considered probable if or when (must have three): (1) it follows a reasonable temporal sequence from administration of the study treatment. (2) It could not readily have been produced by participant's clinical state, environmental or toxic factors, or other therapies administered to the participant. (3) Disappears or is decreased upon discontinuation of the study treatment. (4) It follows a known response pattern to treatment with the study treatment.
- 3. Possibly related:** This category applies to those AEs which, after careful medical consideration at the time they are evaluated, are judged unlikely but cannot be ruled out with certainty to the study treatment. An AE may be considered possible if or when (must have two): (1) it follows a reasonable temporal sequence from administration of the study treatment. (2) It could not readily have been produced by participant's clinical state, environmental or toxic factors, or other therapies administered to the participant. (3) Disappears or is decreased upon discontinuation of the study treatment. (4) It follows a known response pattern to treatment with the study treatment.

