7.4.3. Laboratory Evaluations

Clinical laboratory evaluations include Hematology, Blood chemistry, Urinalysis, Coagulation test.

Laboratory evaluation results of each visit and their changes from baseline will be calculated and summarized in descriptive statistics by treatment group.

Listing by subjects and evaluations will be produced for results from visits and timepoints.

Any abnormal with clinical significance results will be tabulated.

The results of pregnancy test of female subjects will be tabulated.

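### Stopping criteria d to f need a grade and a causality judgement for laboratory abnormalities, but the protocol requires both only for AEs, so a Grade 3 or 4 value called not clinically significant can be missed

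*Protocol*

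**What the plan says.** Protocol 3.1 and the synopsis list the dose-escalation stopping criteria. Criterion d is "The occurrence, in two or more participants of Grade 3 AE or laboratory abnormalities, judged to be probably, possibly, or definitely related to MBS-COV". Criterion e begins "The occurrence of two of the same AE or laboratory abnormality" and applies from Grade 3 upwards. Criterion f applies "in one or more participants of Grade 4 AE or laboratory abnormalities". Both e and f carry the same relatedness condition as d.

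The sections that generate a grade and a relationship are written for AEs. Protocol 9.2.2 says that "the severity of adverse events occurred in this study will be graded", and 9.2.3 says that "AEs will be assigned a relationship (causality) to the study treatment". SAP 4.3.1 repeats both for AEs only.

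Under protocol 9.1, a laboratory abnormality is reported as an AE only when the investigator believes it to be clinically significant. For the rest the instruction is explicit: "Abnormal findings that are NOT clinically significant should not be recorded as an AE".

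Appendix 1, part B gives Grade 1 to 4 limits for laboratory values. In the SAP, 7.4.3 summarises and lists all laboratory results and adds "Any abnormal with clinical significance results will be tabulated". It plans no table by toxicity grade.

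**The concern.** Clinical significance and toxicity grade are different scales, and the protocol never links them. Criteria d to f are framed on grade. Whether a laboratory value acquires the recorded inputs those criteria use depends instead on a prior opinion about clinical significance. If that opinion is negative, the procedure sections do not ask anyone to grade the value or to judge whether it is related.

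This is a first-in-human trial with 6 active participants per cohort in Part A and 8 in Part B. One related Grade 4 abnormality meets f, and two related Grade 3 abnormalities can meet d or e. A value left out for want of a causality entry could therefore decide whether a criterion is recognised as met.

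**Working it through.** The plan states no figure on this point, so the check is of the text.

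**1. Inputs the criteria need.** Each of d, e and f needs (i) a grade and (ii) a judgement of at least possibly related. Each names laboratory abnormalities as an alternative to AEs.

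**2. Where those inputs come from.**

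| Input | AE | Laboratory value not recorded as an AE |
|---|---|---|
| Grade | Required (9.2, 9.2.2; SAP 4.3.1) | Limits exist in Appendix 1 part B; no section requires that they be applied |
| Relationship | Required (9.2, 9.2.3; SAP 4.3.1) | No section requires or records it |
| Review by investigator | Yes | Yes (7.8), with no step to grade or attribute |
| Reaches the SRC | Not itemised; safety data available (3.1, 8.6) | Not itemised; same text |

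**3. The filter.** Section 9.1 routes a laboratory value to the left-hand column only if it is called clinically significant. Otherwise it stays in the right-hand column. There the grade is usually readable from the value, but the relationship is not: no table supplies causality.

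**4. Whether the case can arise.** Inclusion criterion 7 uses abnormal but not clinically significant as an ordinary category for laboratory results. Several Appendix 1 limits concern analytes on the scheduled panel (Table 7-1):
- Grade 3: CPK 3.1 to 10 x ULN, potassium 5.5 to 5.6 mEq/L, a haemoglobin fall of 2.1 to 5.0 g/dL, urine protein 2+, cholesterol above 226.
- Grade 4: potassium above 5.6 mEq/L, PT above 1.25 x ULN.

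Nothing in the protocol says that a value at these grades must be called clinically significant. Nothing says how often it would not be.

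**5. Sensitivity of a small cohort (illustration only).** Let p be the chance that an active participant has a related Grade 3 laboratory abnormality, and q the chance that it is called clinically significant. Both are assumptions; neither is in the documents. Suppose, as the worst case, that values not called clinically significant are never counted. The chance that the laboratory part of criterion d is met among n active participants is then

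P = 1 − (1 − pq)^n − n·pq·(1 − pq)^(n−1).

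- n = 6, p = 0.2: q = 1 gives 1 − 0.262 − 0.393 = 0.345; q = 0.5 gives 1 − 0.531 − 0.354 = 0.114.
- n = 8, p = 0.2: q = 1 gives 0.497; q = 0.5 gives 0.187.
- For p from 0.1 to 0.3, moving q from 1 to 0.5 changes the range from 0.114–0.580 to 0.033–0.224 (n = 6), and from 0.187–0.745 to 0.057–0.343 (n = 8).

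This shows only that cohorts of this size are sensitive to a filter. It does not estimate anything about this trial.

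**The case against.** The best reply is that the criteria themselves call for the judgement. They name laboratory abnormalities, they say judged related, and they do not tie that judgement to the AE form. Section 9.2.3 says that AEs get a causality assessment; it does not forbid one for anything else. Appendix 1 part B grades mostly by number, so the SRC could read off most grades. All results go on the CRF (SAP 4.3.2), and protocol 8.7.8.2 lists and summarises abnormal results without a clinical-significance filter. The SRC reviews the safety data of every completed cohort (8.6). Criterion g lets it act on a pattern of individually minor findings. Even when a criterion is met, the SRC makes the final recommendation.

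Much of this stands. A reader might infer that a value not called clinically significant cannot meet d to f, that the laboratory trigger collapses into the AE trigger, or that the relatedness assessment is never made. The documents do not support that: they leave the assessment unassigned, not barred. Nor do they show that the SRC would receive no graded results, since the content of its data package is not described.

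What the reply does not provide is a source for the relationship. Listings carry no causality, and the SAP outputs are planned for the final analysis. Criterion g concerns a pattern that the investigator regards as a safety concern, not a single Grade 4 value or two Grade 3 values.

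A reader might also size the problem by counting scheduled post-dose panels: 4 × 24 + 9 × 20 = 276. That is not a measure of it. The count covers all panels, not Grade 3 or 4 values called not clinically significant. It includes placebo participants, and it includes the Day 14 visit, which follows the Day 7 or Day 9 point at which escalation may be decided.

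**Conclusion.** The concern holds as a gap between the escalation criteria and the procedures meant to feed them. The causality gap is firm: for a laboratory value that is not an AE, no section requires or records a relationship, yet d to f depend on one. The grade gap is weaker and procedural, because the limits exist but only AEs must be graded. The consequence is that a Grade 3 or 4 value can be missed, not that it will be.

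No magnitude can be stated, because the documents give no rate for such values. The conclusion rests on 9.1 being followed as written and on no instruction in a document outside the protocol and SAP filling the gap. It should be corrected, because the criteria govern escalation in a first-in-human trial and the correction is small.

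**What to change.** Reconcile 9.1, 9.2.2 and 9.2.3 with criteria d to f:

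- **9.2.2:** state that post-dose laboratory results are graded against Appendix 1 regardless of the clinical-significance call, subject to that appendix's caveats on institutional reference ranges and on symptoms that raise a grade.
- **9.2.3:** state that the investigator records a relationship for each new or worsened laboratory result of Grade 3 or higher, even if it is not recorded as an AE.
- **3.1 or 8.6:** state that a listing of these results, with grade and relationship, goes to the SRC at each review.
- **SAP 4.3.1 and 7.4.3:** carry the same provisions and add the listing.

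The criteria, the grade thresholds and any clinical action that follows are left to the sponsor.

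The cost is a few sentences, one CRF field and one listing. The downside is some extra causality calls, including for low Appendix 1 limits such as those for cholesterol and urine protein.

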9.2. REPORTING OF ADVERSE EVENTS (AEs)

The Investigator will then record all relevant AE/SAE information in the eCRF. All AEs will be collected from the time of dose administration until the safety follow-up visit. Medical occurrences that occur before the start of the study treatment, but after obtaining the ICF will be recorded in the Medical History section of the eCRF and not in the AE section, unless considered related to the study procedures. All events will be followed to resolution or until the participant completes the study. A final assessment of outcome will be made at that time.

All AEs must be recorded in the participant's medical records and on the CRF. AEs will be reported using customary medical terminology along with the following information: the onset and end dates, whether the event is considered to be a SAE (see [Section 9.3](#)), the impact the event had on study treatment (see [Section 9.2.1](#)), the Toxicity Grading Scale (intensity) of the event (see [Section 9.2.2](#)), the causality of the event (see [Section 9.2.3](#)), whether treatment is given as a result of the event (see [Section 9.2.4](#)), and the outcome of the event (see [Section 9.2.5](#)).

9.2.1. Impact on Study Treatment

The impact the event had on the study treatment will be assessed as either: dose increased, dose not changed, dose rate reduced, dose reduced, drug interrupted, drug withdrawn, not applicable, or unknown. The "not applicable" assessment will be used only when the participant is no longer in the Treatment Phase of the protocol.

9.2.2. Toxicity Grading Scale (Intensity) Assessment

According to the guideline of “Toxicity Grading Scale for Healthy Adult and Adolescent Volunteers Enrolled in Preventive Vaccine Clinical Trials” issued by FDA, the severity of adverse events occurred in this study will be graded. The general guidelines for assessing the AE grade refer to appendix 1.

9.2.3. Event Causality Assessment

AEs will be assigned a relationship (causality) to the study treatment. The Investigator will be responsible for determining the relationship between an AE and the study treatment. The type of event, organ system affected, and timing of onset of the event will be factors in assessing the likelihood that an AE is related to the study treatment. Relationship of AEs to study treatment will be classified as follows:

- 1. Definitely related:** This category applies to those AEs that the Investigator feels are incontrovertibly related to the study treatment. An AE may be assigned an attribution of definitely related if or when it meets all of the following criteria: (1) it follows a reasonable temporal sequence from administration of the study treatment; (2) it could not be reasonably explained by the known characteristics of the participant's clinical state, environmental or toxic factors, or other modes of therapy administered to the participant; (3) it follows a known response pattern to treatment with the study treatment.
- 2. Probably related:** This category applies to those AEs which, after careful medical consideration at the time they are evaluated, are felt with a high degree of certainty to be related to the study treatment. An AE may be considered probable if or when (must have three): (1) it follows a reasonable temporal sequence from administration of the study treatment. (2) It could not readily have been produced by participant's clinical state, environmental or toxic factors, or other therapies administered to the participant. (3) Disappears or is decreased upon discontinuation of the study treatment. (4) It follows a known response pattern to treatment with the study treatment.
- 3. Possibly related:** This category applies to those AEs which, after careful medical consideration at the time they are evaluated, are judged unlikely but cannot be ruled out with certainty to the study treatment. An AE may be considered possible if or when (must have two): (1) it follows a reasonable temporal sequence from administration of the study treatment. (2) It could not readily have been produced by participant's clinical state, environmental or toxic factors, or other therapies administered to the participant. (3) Disappears or is decreased upon discontinuation of the study treatment. (4) It follows a known response pattern to treatment with the study treatment.
- 4. Unlikely related:** In general, this category can be considered applicable to those AEs which, after careful medical consideration at the time they are evaluated, are judged likely to be unrelated to the study treatment. An AE may be considered unlikely if or when (must have two): (1) it does not follow a reasonable temporal sequence from administration of the study treatment. (2) It could not readily have been produced by participant's clinical state,

environmental or toxic factors, or other therapies administered to the participant. (3) Disappears or is decreased upon discontinuation of the study treatment. (4) It does not follow a known response pattern to treatment with the study treatment.

5. **Unrelated:** This category applies to those AEs which, after careful consideration at the time they are evaluated, are clearly and incontrovertibly due to extraneous causes (disease, environment, etc.) and determined with certainty to have no relationship to the study treatment.

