1.4.2. Clinical Studies

The current proposed study is a first-in-human study to evaluate the safety, tolerability, and PK of inhaled MBS-COV.

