Since the safety profile of MBS-COV in humans is unknown and this is the first clinical study to assess MBS-COV in humans, phase I clinical study for MBS-COV will be divided into two parts. Part A is a randomized, double-blind, and placebo-controlled study with single ascending dose (SAD) design of inhaled MBS-COV in healthy participants for determining safety, tolerability, and pharmacokinetics of MBS-COV. Part B will be performed after review of sufficient result of Part A. Part B is a randomized, double-blind and placebo-controlled study with multiple ascending doses (MAD) of inhaled MBS-COV in healthy participants to evaluate safety, tolerability, and pharmacokinetics.

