4.2.3. Part A (SAD) - Treatment Visit 1: Baseline Visit (T1: Day 1)

The first assigned study treatment dose will be administered after completion of all study evaluations. Adverse events and changes in concomitant medications will be collected. Participants in Cohorts A1 to A3 will be inhaled a single dose of MBS-COV or placebo through a portable nebulizer on Day 1.

The following assessments will be performed:

- Medical history (pre dose)
- Vital signs (pre and post dose) (Vital signs will include blood pressure, pulse, respiration rate, and temperature. On treatment visits will be conducted three times a day, within 120 minutes before administration, within 1 hour after administration, and 4-6 hours after administration, respectively.)
- Randomization (pre dose)
- Physical examination (pre and post dose)
- 12-lead ECG (pre and post dose) (12-lead ECG on treatment visits will be conducted three times a day, within 120 minutes before administration, within 1 hour after administration, and 4-6 hours after administration, respectively.)
- List concomitant medications
- PK timepoints: Cohorts A1 to A3: For the single dose on day 1, blood samples will be collected before dosing, and afterwards at 5 min (± 1 min), 15 min (± 2 min), 0.5 h (± 2 min), 1 h (± 5 min), 2 h (± 5 min), 4 h (± 5 min), 8 h (± 10 min), 10 h (± 10 min) after dosing.
- ADA timepoints: Blood samples will be collected on Day 1 before dosing
- Spirometry Assessment (Spirometry assessments will be started 5 minutes after the dosing with frequent spirometry measurements at 5 (± 1 min), 15 (± 1 min), 30 (± 5 min), 60 minutes (± 5 min).)

- Adverse events evaluation after first dose
- Participants will be confined till 24 hours pharmacokinetic samples are obtained following study drug administration.

4.2.4. Part A (SAD) – Treatment Visit 2 to Treatment Visit 5/End of Treatment (T2: Day 2 to T5: Day 7)

The following assessments will be performed (refer to the schedule of events Table 4-1)

- Vital signs
- Physical examination, including dermatologic examination
- 12-lead ECG
- List concomitant medications
- Laboratory assessments (hematology, chemistry, coagulation and urine analysis) (T2, T3, and T5 only)
- Chest X-ray (T5 only)
- PK timepoints: Cohorts A1 to A3: For the single dose on day 1, blood samples will be collected at 24 h (\pm 10 min) and 48h (\pm 10 min) after dosing.
- Serum pregnancy test only on T5 (EOT)
- Adverse events evaluation

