The PI's (or designee's) assessment of an AE's relationship to study drug is part of the documentation process. The evaluation of relationship is based on the following 5 levels: Definitely related, Probably related, Possibly related, Unlikely related, Unrelated and will be recorded on CRF. The adverse events been evaluated the relationship to drug as Definitely related, Probably related, Possibly related will be referred to treatment related adverse event. The detailed definition and guidelines of 5 level relationship (Definitely related, Probably related, Possibly related, Unlikely related, Unrelated) of adverse event to study drug can be referred on protocol section 9.2.3.

Grading AE by Severity

According to the guideline of "Toxicity Grading Scale for Healthy Adult and Adolescent Volunteers Enrolled in Preventive Vaccine Clinical Trials" issued by FDA, the severity of adverse events occurred in this study will be graded. The general guidelines for assessing the AE

grade refer on protocol appendix 1.

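### The item counts in Protocol 9.2.3 contradict the section's own category descriptions and give no single answer at the boundary between related and not related

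*Protocol*

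**What the plan says.** Protocol 9.2.3 gives each causality category an opening description and then a rule.

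- **Definitely:** "An AE may be assigned an attribution of definitely related if or when it meets all of the following criteria". There are three: timing, no reasonable alternative, and "3) it follows a known response pattern to treatment with the study treatment".
- **Probably:** three of four items, namely plausible timing, no ready alternative, and "3) Disappears or is decreased upon discontinuation of the study treatment. (4) It follows a known response pattern to treatment with the study treatment".
- **Possibly:** two of the same four. Its description is of an event thought improbable but not excludable.
- **Unlikely:** two of four. Item 1 is reversed (poor timing), and so is item 4: "4) It does not follow a known response pattern to treatment with the study treatment". Items 2 and 3 are worded as they are under Probably and Possibly.
- **Unrelated:** no count, but it requires certainty of an extraneous cause.

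On prior experience, Protocol 1.4.2 states: "The current proposed study is a first-in-human study to evaluate the safety, tolerability, and PK of inhaled MBS-COV". Protocol 1.6 opens its last paragraph with "Since the safety profile of MBS-COV in humans is unknown". On Part A dosing, Protocol 4.2.3 states: "Participants in Cohorts A1 to A3 will be inhaled a single dose of MBS-COV or placebo through a portable nebulizer on Day 1".

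SAP 4.3.1 refers to 9.2.3 for the definitions and pools three levels: "Definitely related, Probably related, Possibly related will be referred to treatment related adverse event". Stopping criteria a to f in Protocol 3.1 pool the same three.

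**The concern.** Two of the four items are hard to apply in Part A. After one dose there is ordinarily nothing left to discontinue, and a drug with no prior human use has no documented human response pattern. Section 9.2.3 does not say how to score an item that cannot be assessed, or what source may supply a known pattern. Separately, two Unlikely items point the same way as in the related categories, so evidence for a drug effect also counts towards Unlikely.

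Both faults act on the one distinction that the analysis uses, related against not related. That distinction defines the incidence of treatment-related AEs (Protocol 2.2.1; SAP 4.1.1 and 4.2.1), the related-AE tables in SAP 7.4.2, and stopping criteria a to f. Two investigators who follow the text faithfully could classify the same event differently.

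**Working it through.** No figure in the plan needs reproducing. The check scores every combination of items against the rules in Protocol 9.2.3.

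**Notation (1 = met, 0 = not met).** T = plausible timing; A = no ready alternative; D = abates on discontinuation; K = follows a known response pattern. The slightly different wording of the alternative-cause item under Definitely is treated as the same A.

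**Rules.** Related count R = T + A + D + K. Unlikely count U = (1−T) + A + D + (1−K). Definitely: T, A and K all 1. Probably: R ≥ 3. Possibly: R ≥ 2. Unlikely: U ≥ 2.

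| T A D K | R | U | Counted categories met |
|---|---|---|---|
| 1 1 1 1 | 4 | 2 | Definitely, Probably, Possibly, Unlikely |
| 1 1 1 0 | 3 | 3 | Probably, Possibly, Unlikely |
| 1 1 0 1 | 3 | 1 | Definitely, Probably, Possibly |
| 1 1 0 0 | 2 | 2 | Possibly, Unlikely |
| 1 0 1 1 | 3 | 1 | Probably, Possibly |
| 1 0 1 0 | 2 | 2 | Possibly, Unlikely |
| 1 0 0 1 | 2 | 0 | Possibly |
| 1 0 0 0 | 1 | 1 | none |
| 0 1 1 1 | 3 | 3 | Probably, Possibly, Unlikely |
| 0 1 1 0 | 2 | 4 | Possibly, Unlikely |
| 0 1 0 1 | 2 | 2 | Possibly, Unlikely |
| 0 1 0 0 | 1 | 3 | Unlikely |
| 0 0 1 1 | 2 | 2 | Possibly, Unlikely |
| 0 0 1 0 | 1 | 3 | Unlikely |
| 0 0 0 1 | 1 | 1 | none |
| 0 0 0 0 | 0 | 2 | Unlikely |

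Eight combinations meet both Unlikely and a related category, 2 meet none, 3 are related only and 3 are Unlikely only (8 + 2 + 3 + 3 = 16). The first row needs no special reading: an event that meets every item for a drug effect also meets Unlikely through items 2 and 3.

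**Part A.** The answer depends on how D and K are read. Cells give R/U and the categories met.

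| Event | D and K unmet, reversed K counted | D and K unmet, reversed K not counted | Recovery after the dose counted as D | Nonclinical or earlier-cohort pattern counted as K |
|---|---|---|---|---|
| Well timed, no alternative | 2/2: Possibly and Unlikely | 2/1: Possibly | 3/3: Probably, Possibly and Unlikely | 3/1: Definitely, Probably, Possibly |
| Well timed, uncertain alternative | 1/1: none | 1/0: none | 2/2: Possibly and Unlikely | 2/0: Possibly |
| Poorly timed, no alternative | 1/3: Unlikely | 1/2: Unlikely | 2/4: Possibly and Unlikely | 2/2: Possibly and Unlikely |
| Poorly timed, uncertain alternative | 0/2: Unlikely | 0/1: none | 1/3: Unlikely | 1/1: none |

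The second row is the important one. The same event is unclassifiable, both Possibly and Unlikely, or Possibly alone, according to how undefined terms are read.

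**Scale.** Part A has 24 of the 44 participants and 3 × 6 = 18 of the 18 + 2 × 8 = 34 on active drug. With 6 active per cohort, one reclassified participant moves related-AE incidence by 1/6 = 16.7 percentage points. Stopping criterion d needs two participants.

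**The case against.** The strongest reply is that causality is the investigator's judgement. Section 9.2.3 tells the investigator to weigh event type, organ system and timing, and introduces the counts permissively. That softens the defect but does not remove it. The counts themselves are stated as requirements, and if judgement overrides them they serve no purpose. The descriptions do not settle the matter either, because Possibly (improbable but not excludable) and Unlikely (probably not related) lie close together.

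A reader might infer that Probably and Definitely cannot be reached in Part A. The documents do not establish that. The pattern item is not restricted to human data: Protocol 1.4.1 reports a lung finding in hamsters, and earlier cohorts are reviewed before escalation. Dosing is by nebulizer, and Protocol 9.2.1 lists interruption as a recordable impact, so discontinuation is not wholly empty. Crediting recovery after the dose makes Probably reachable, and crediting a pattern makes Definitely reachable. In any case, losing those two levels alone would change no related-AE count and would not affect stopping criteria a to f, because the three levels are pooled.

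A reader might also infer that any well-timed event with another explanation goes unclassified. That is too wide: a certain extraneous cause fits Unrelated. The gap concerns uncertain alternatives.

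There are safeguards. All AEs are summarised regardless of causality (Protocol 8.7.8.1; SAP 7.4.2), criterion g rests on the Safety Review Committee's own judgement of relatedness, and criterion h needs no causality. These limit the harm, but they do not repair the primary outcome or criteria a to f.

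**Conclusion.** The point holds as a defect at the related/not-related boundary, and it should be fixed. Section 9.2.3 contradicts its own description of Possibly, and its counts are neither exclusive nor exhaustive: 8 of 16 combinations meet both Unlikely and a related category, and 2 meet none.

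The gap for a well-timed event with an uncertain alternative in Part A assumes that the discontinuation and pattern items are not met. The overlap for a well-timed event with no alternative assumes, in addition, that the reversed pattern item counts as met. The general overlap needs neither assumption.

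The 16 combinations are logical possibilities, not frequencies. The documents give no basis for estimating how many events would be affected, or for claiming a net bias in one direction. The 16.7 points is the effect of one participant, not an expected error.

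**What to change.** Amend Protocol 9.2.3 as follows.

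1. Make the Possibly rule agree with its description: plausible timing, where the study treatment cannot be excluded, qualifies even if another explanation exists.
2. Reverse Unlikely items 2 and 3, so that a ready alternative, and failure to abate after dosing stops, count towards Unlikely.
3. State how the discontinuation and pattern items are scored when they cannot be assessed (single dose, no prior human data). A non-assessable item should count neither for nor against relatedness.
4. Make the categories exclusive and exhaustive, and keep Probably and Definitely distinguishable.

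Reversal alone is not enough. With all four items reversed, U = 4 − R, so both thresholds are still met whenever R = 2, which is 6 of the 16 combinations (4 × 3 / 2). With D and K set aside in Part A, a well-timed event with an uncertain alternative would still score 1 and 1. Changes 1, 3 and 4 are therefore needed as well.

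Simply deleting the pattern item and voiding the discontinuation item would not do. Unlikely would then need poor timing together with no ready alternative, and Definitely would become nearly the same as Probably.

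SAP 4.3.1 already refers to 9.2.3, so it follows automatically. The cost is protocol wording and any matching CRF guidance. The downside is that somewhat more events will be classed as treatment-related.
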